## 1. STUDY PURPOSE AND RATIONALE

More than one million people are living with HIV in the United States and an estimated 56,300 Americans become infected with HIV each year. Domestically, men who have sex with men (MSM) remain the population most severely affected by HIV, accounting for more than 50% of all new infections in the US each year, and just under half (48%) of people living with HIV. Furthermore, new HIV diagnoses among MSM are more than 44 times that of other men (1). In New York City, the AIDS case rate is almost 3 times the United States average and MSM remain an important risk group (2). It is evident that risk reduction strategies for this population are imperative. While condom use is effective in HIV prevention, current strategies, such as educational programs, have not significantly reduced HIV incidence (3).

A recent press release from the CDC announced that adolescents and young MSM (age 13-29) of all races are severely affected by the HIV epidemic, but young black MSM are the only group to demonstrate a statistically significant increase in the number of HIV infections from 2006 to 2009. It is estimated that HIV infection rates increased by 48% for this group during this four-year period. In 2009, infection rates among all blacks and Hispanics were nearly 8 times and 3 times the rate of whites, respectively (4). High prevalence of HIV in these minority communities means that uninfected members of these communities are at higher risk of infection with every sexual encounter. New biomedical methods of HIV prevention can be utilized to target these high-risk populations, and must be assessed and used strategically in order to reduce the prevalence and rates of infection among these communities.

Biomedical strategies focusing on the use of antiretroviral (ART) drugs for prevention of HIV acquisition are an important strategy. Much of the data supporting use of pre-exposure prophylaxis (PrEP), are based on both animal models and studies in humans showing the effectiveness of post-exposure prophylaxis (PEP). The goal of ART administered as PEP and PrEP is to prevent the HIV virus from establishing around the time of exposure. The key difference between the two is that while one presumes exposure is infrequent and unpredictable (PEP), the other anticipates regular exposures to HIV (PrEP). The CDC currently recommends PEP after occupational or non-occupational exposure to HIV-infected fluids (5).

Pre-exposure prophylaxis (PrEP) is one of the new biomedical prevention techniques that has recently demonstrated efficacy in reducing HIV acquisition in MSM, high-risk heterosexual men and women, and serodiscordant couples. PrEP stands for Pre-Exposure Prophylaxis, an experimental approach to HIV

prevention where HIV negative people take HIV drugs to try to prevent HIV infection. PrEP is started **before** being exposed to HIV and continued during periods of risk. This is different from post-exposure prophylaxis (PEP) where the medication is started soon **after** exposure to HIV and continued for 28 days. PrEP can be in the form of a pill taken by mouth or a gel applied in the vagina or rectum. Current studies of oral PrEP (pills) have tested the HIV drug Tenofovir (also known as Viread) alone or in combination with emtricitabine (the combined drug is also known as Truvada) as a daily pill. Both tenofovir and Truvada are approved for the treatment of HIV infection in HIV-positive people. Preventing an infection by giving a drug that is also used to treat that infection has been a successful approach against other diseases such as malaria.

To date, results from four large efficacy studies have reported on the effectiveness of preventing HIV acquisition with oral PrEP. The results of 3 of the studies are very encouraging and show that taking an anti-HIV pill daily can be partially effective in protecting from HIV.

These efficacy studies include:

**iPrEx:** conducted among MSM and transgender women who have sex with men in South America, South Africa, Thailand and USA. The primary analysis of the iPrEx study were reported in the 4th quarter of 2010 and represents the first efficacy results of oral PrEP with once-daily TDF-FTC (Truvada). In the study there was a relative risk reduction in HIV acquisition of 44% among MSM and transgender women who have sex with men in combination with comprehensive prevention services such as monthly HIV testing, condom provision, counseling, and treatment of other sexually transmitted infections. The reduction of HIV-1 acquisition was strongly correlated with adherence measured by self-report and pill count/dispensing; for example a 73% reduction was noted at adherence levels greater than or equal to 90%. Furthermore, risk behavior among participants declined overall during the trial with respect to the number of sexual partners and condom use, which was likely a result of the risk reduction counseling provided as part of the trial (7).

**FemPrep:** conducted among 1951 women in Kenya, Tanzania, and South Africa. After a regularly scheduled interim review of the data in April 2011, Independent Data Monitoring Committee (IDMC) recommended stopping the study because Truvada was not effective in reducing the risk of HIV infection. There were a total of 56 new HIV infections in the study. An equal number of infections occurred in participants assigned to Truvada and those assigned to a placebo pill. Retention was very high in the study (about 90%) and self-reported adherence to the medication was high at about 95%. It is not clear why Truvada was not effective in preventing HIV infection in this study. The data will be looked at more closely. But possible explanations include low adherence to the study pill, study pill sharing between the participants in the Truvada and placebo groups, chance, or some biological reasons, or a combination of these factors (8).

**PARTNERS PrEP:** a study of daily Tenofovir or Truvada pill conducted among serodiscordant heterosexual couples (one partner is HIV+) in Kenya and Uganda. In July 2011, after review of the study by the Data and Safety Monitoring Board, it was announced that Tenofovir and Truvada taken daily reduced the risk of HIV transmission among both men and women. In the trial, daily oral TDF reduced HIV risk by an estimated 62 percent infections and daily oral TDF/FTC reduced HIV risk by an estimated 73 percent (95% CI 49 to 85,  $p < 0.0001$ ) when compared to a placebo. Both drugs were effective in both men and women, and there were no significant safety events in the trial (9).

**TDF2:** conducted among 1,219 heterosexual male and female participants in Botswana. In this trial, PrEP using daily oral Truvada was found to reduce the risk of HIV infection by approximately 63 percent (95% CI 21.5 to 83.4,  $p = 0.0133$ ) among heterosexual men and women overall when compared to placebo. The data suggests efficacy for both men and women, but definitive conclusions cannot be drawn by gender due to the limited size of the study. Overall safety and efficacy findings are consistent with the Partners PrEP data, with only nausea, vomiting, and dizziness reported at significantly higher rates using Truvada

versus placebo (9).

While the results of these studies are promising, many questions remain regarding its application to clinical practice, the long-term safety of this regimen, and development of resistance to FTC/TDF, which is an important component of the preferred initial antiretroviral regimen in the US. Several ongoing studies of systemic and topical PrEP, administered daily or intermittently, will provide important answers for the field and will inform normative guidelines (10, 11). At present, however, PrEP would only be available through prescriptions and its use is dependent on patients' knowledge, attitudes, and acceptability of PrEP. This may serve as a barrier to the implementation of PrEP if education on its efficacy is not a routine part of clinical practice. Prior to the publication of these PrEP efficacy results, surveys conducted among at-risk MSM document limited knowledge of PrEP but high level of interest in considering its use (12,13). Now that there is hard evidence demonstrating partial efficacy of PrEP in preventing HIV infection, a study assessing patients' knowledge, attitudes, and intent to use PrEP based on these results is needed.

Identification of these barriers and limitations can help develop interventions that raise awareness among at risk adolescent and young adults about the use of anti-retrovirals to prevent HIV acquisition. Providing knowledge about these recent studies will be essential prior to successful implementation of PrEP as a public health strategy. Individual counseling on patient education has demonstrated to be effective in changing behavior, including smoking in diabetic patients (14). One-on-one counseling may also address patient and provider concerns (i.e. side effects, possibility of developing resistant strains, increase in risky behavior). Given the burden of HIV in New York City, characterization of barriers to the implementation of this prevention strategy and the method in which we should educate at-risk populations about PrEP is of great importance.

## 2. STUDY DESIGN AND STATISTICAL PROCEDURES

We propose to survey HIV negative young adults (age 18-25) waiting to see their providers at Project Stay, a Columbia-affiliated clinic for high-risk youth. After obtaining demographic information, including health insurance status, education level, and sexual health, participants will be asked about their baselines knowledge, attitudes, and willingness to use PrEP. They will then be educated on the recent PrEP results by randomization to either the control group (given a pamphlet on PrEP) or the intervention group (a one-on-one counselor session + the pamphlet on PrEP). Randomization will include stratifying by MSM demographic using a block randomization put together by a third-party. The counselor will be blinded to which arm the participant will be randomized to until the survey has been completed. After their educational intervention, they will see their provider, who will be asked if the participants inquired about PrEP or if the provider brought up the subject him or herself, and if the participant had asked for a prescription. One week following their appointment, they will be e-mailed an electronic survey asking them the same questions on their knowledge, attitudes, and willingness to use PrEP. Finally, we will assess the number of prescriptions for PrEP that were prescribed/filled at 0 months, 6 months, and 1 year. In addition to elucidating baseline willingness to use PrEP and how different modes of education can influence knowledge, interest, and uptake, we also aim to measure the acceptability of other methods of HIV prevention, including alternative ways to administer PrEP, including vaginal and rectal microbicides, IM injection, intermittent oral PrEP use, condoms, circumcision, and vaccines.

The primary research questions are as follows:

Primary Objective #1: To determine if one-on-one counseling on recent PrEP results can increase the proportion of high-risk adolescent and young adults who ask their providers for PrEP

Primary Objective #2: To determine if one-on-one counseling on recent PrEP results can increase the proportion of high-risk adolescent and young adults who are prescribed PrEP and have filled prescriptions at 0, 6, and 12 months.

Secondary Objective #1: To determine current knowledge, attitudes, and willingness to use PrEP for HIV prevention amongst high-risk adolescents and young adults age 18-25 in light of recently announced oral PrEP study results.

Secondary Objective #2: To determine specific concerns or barriers (e.g., concerns about potential side effects, concerns that I would increase risk taking behavior, don't feel that I am at risk for HIV, don't like taking pills, don't think the pill will protect me from getting HIV infected, concerns that if HIV medications are used now, they won't work in the future if I became HIV+, concerns that others might think I am HIV positive, concerns this would limit the availability of HIV medications for people infected with HIV, already using a strategy for prevention that is effective, concerned it is too expensive) that would prevent high-risk adolescents and young adults to use oral PrEP, and how this may be influenced by different modes of education.

Secondary Objective #3: To assess the acceptability of various methods of HIV prevention, including variations in the timing and way of administering PrEP (i.e. via IM, via microbicides, or intermittent dosing).

Statistical analysis of the questionnaire survey data will be performed using SAS software. Frequencies of responses to survey questions will be described. Chi square and Fisher's exact tests will be computed to compare pamphlet-educated participants' survey responses and PrEP prescriptions to the responses and prescriptions of participants educated by one-on-one counseling. Variables with p-value < 0.05 will be considered significant and will be included in multivariate logistic regression model. Forward selection will be used in the logistic regression model to evaluate variables independently associated with willingness to use PrEP. The outcome variables, whether or not they would use PrEP and bring the issue up with their provider, will be evaluated using a proportion and compared between groups; PrEP prescriptions written and filled at 0, 6, and 12 months will also be evaluated, proportion will be computed and then compared between groups.

The primary endpoint is the difference between the proportion of participants who asked their providers about PrEP in the intervention group versus control group. Because of the limited ability to survey 100 participants (50 in each group), we will use this fixed number of subjects in our power analysis to determine the smallest difference for which the available number of subjects will lead to statistical significance.

A study in Boston found that 74% of MSM were interested in using PrEP after being educated in-person about its potential (12). Based off this information, one can assume that the proportion of those willing to use PrEP will be approximately 74% for the group with one-on-one counseling (+ pamphlet) on the recent PrEP results, and could lead to a corresponding 74% who will ask their providers about it. Using backward power calculation using our predetermined sample size of 50 in each group, with  $\alpha = .05$  and power = .80, we would find a difference between the two groups if the proportion of those who ask their provider about PrEP in the control group is < .46 (or > .96). Thus, the smallest difference for which our study will find a statistical difference between each group is .28.

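### The protocol fixes chi-square and Fisher's exact tests for every survey comparison between arms, which would be inefficient for knowledge taken as a whole and for any item with ordered answers

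*Protocol*

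**What the plan says.** All the relevant text is in Section 2 of the protocol (Study Design and Statistical Procedures).

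- Description of the survey data: "Frequencies of responses to survey questions will be described".
- Comparison of arms: "Chi square and Fisher's exact tests will be computed to compare pamphlet-educated participants' survey responses and PrEP prescriptions to the responses and prescriptions" of the participants counselled one-on-one. No rank, ordinal or mean-based comparison is named.
- Willingness and asking the provider: "The outcome variables, whether or not they would use PrEP and bring the issue up with their provider, will be evaluated using a proportion", then compared between groups. Willingness also enters a regression, still as a binary outcome: "Forward selection will be used in the logistic regression model to evaluate variables independently associated with willingness to use PrEP".
- Aim: the study is to show "how different modes of education can influence knowledge, interest, and uptake". Secondary Objective #2 likewise asks whether mode of education influences barriers.
- Measurement: one week after the visit, "they will be e-mailed an electronic survey asking them the same questions on their knowledge, attitudes, and willingness to use PrEP". Section 3 (Study Procedures) again speaks of questions on these domains. Section 5 (Study Instruments) lists two attached questionnaires.
- Primary endpoint: "The primary endpoint is the difference between the proportion of participants who asked their providers about PrEP in the intervention group versus control group". This is yes/no by nature.

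**The concern.** The aim for knowledge is a between-arm question: do counselled participants know more than those given the pamphlet alone? How much someone knows is naturally a total over several questions. A chi-square test applied to each response never tests that total. It leaves a list of item-level p-values and no single answer for the domain.

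A Pearson chi-square or Fisher's exact test on more than two categories also treats them as unordered. If an attitude, willingness or acceptability item has graded answers, a consistent shift towards the favourable end is spread over several degrees of freedom and is harder to detect.

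The sample is fixed by feasibility at 50 per arm. The one-week survey relies on e-mail reply, so 50 is its ceiling. A more efficient analysis of data already collected is one of the few ways left to gain power on these outcomes.

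**Working it through.** **Inputs from the protocol (Section 2).** 50 per arm; α = .05; power .80; 74% in the counselled arm; detectable control proportion below .46 (or above .96); smallest difference .28. Two-sided testing is implied, because limits are given in both directions.

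**Inputs assumed.** Item format, number of knowledge items, percentage correct, correlation between items, and follow-up response. The protocol gives none of these.

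**1. The plan's own figure.** It concerns asking the provider, a binary outcome. With p̄ = (.74 + .46)/2 = .60:
- pooled SE = √(2 × .60 × .40/50) = .0980
- unpooled SE = √((.74 × .26 + .46 × .54)/50) = .0939
- power = Φ((.28 − 1.96 × .0980)/.0939) = Φ(0.937) ≈ 82.6%

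Solved for exactly 80% power, the lower control limit is .469, a difference of .271. The stated .46 and .28 are within .01 of this. The upper limit comes out at .942 against the stated .96. That mismatch does not bear on this point.

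**2. An ordered item.** For illustration, take .74 versus .46 as the yes/no split of a graded item under proportional odds. The shift is ln(.74/.26) − ln(.46/.54) = 1.046 + 0.160 = 1.206, an odds ratio of about 3.3. Simulated power (3,000 replicates; simulation standard error near 83% is √(.83 × .17/3000) ≈ 0.7 points):

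| Setting | Yes/no chi-square | Chi-square on all levels | Wilcoxon |
|---|---|---|---|
| 50 per arm, 4 levels | 83% | 78% | 90% |
| 50 per arm, 5 levels | 83% | 77% | 92% |
| 35 per arm, 4–5 levels | 68% | 56–61% | 78–79% |

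At 50 per arm the rank test gains 90 − 83 = 7 to 92 − 83 = 9 points over the split, and 90 − 78 = 12 to 92 − 77 = 15 over the unordered test. A repeat simulation gave 82–83%, 74–78% and 90%, which puts the second gain at up to 90 − 74 = 16. With three levels, Wilcoxon gains only about 2 points over the split and 8 over the three-level chi-square.

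**3. A different effect model.** Five equally likely levels in the control arm, 50 per arm, 6,000 replicates. Odds ratios of 2.0, 2.5 and 3.0 give Wilcoxon 49%, 72% and 86%; unordered chi-square 30%, 50% and 65%; binary split 43%, 64% and 79%. The gains are 6 to 8 points over the split and 19 to 22 over the unordered test. With 40 per arm and odds ratio 2.5, the figures are 62%, 39% and 55%. The direction is the same; the size depends on the model.

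**4. Knowledge.** Assume 50% versus 65% correct per item, 50 per arm. For one item, p̄ = .575:
- pooled SE = √(2 × .575 × .425/50) = .0989
- unpooled SE = √((.25 + .2275)/50) = .0977
- power = Φ((.15 − 1.96 × .0989)/.0977) = Φ(−0.45) ≈ 33%

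Simulation gives 34–35%. A Wilcoxon test on the total score, with latent inter-item correlation from .6 down to .2, gives 53–72% with four items and 59–87% with eight. Across repeat runs the full range is about 52–88%.

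**The case against.** The strongest objection is that the instrument is not in view. No section mentions a knowledge score, a graded scale or any ordered answer. The visible text leans towards categorical data: the barriers in Secondary Objective #2 are separate statements, and willingness is worded as whether or not the participant would use PrEP. If the items are yes/no or nominal, the named tests are suitable. This stands, and it is why the loss can only be stated conditionally. Even the existence of several knowledge questions is a natural reading rather than a proven one, since the plural covers knowledge, attitudes and willingness together.

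A reader might infer that the protocol takes a graded willingness scale and cuts it to yes/no. The documents do not support that: no finer scale is shown, and the question may simply be yes/no. Nor are .74 and .46 willingness rates for the two arms. The 74% starts as an interest figure from the Boston study, but the protocol carries it over to asking the provider, and .46 is the detectable control limit for that outcome.

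It can also be said that scoring rules belong in a statistical analysis plan, which is not shown. That is fair for how a score is built. It does not dispose of the point, because the protocol itself names the test for survey responses without restriction.

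Three further limits stand. Secondary Objective #1 is worded descriptively ("To determine current knowledge, attitudes, and willingness to use PrEP for HIV prevention amongst high-risk adolescents and young adults age 18-25"), so the between-arm aim for knowledge rests on the general aim in Section 2. Proportional odds favours the rank test. And 35% is the power for one given item: testing several gives more chances of some significant result, but at an uncontrolled error rate, up to 1 − .95⁴ ≈ 19% for four independent items and 1 − .95⁸ ≈ 34% for eight.

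**Conclusion.** The point holds in conditional form. The protocol fixes an unordered, response-by-response comparison for all survey data, while its aim for knowledge calls for one between-arm answer. The named tests lose power for a multi-item knowledge domain and for any ordered item.

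For ordered items the loss is modest against a yes/no split and larger against an unordered chi-square; with three levels it is close to nil against the split. For knowledge the gain from a score is larger, but it rests entirely on assumed percentages correct, item counts and correlations. Where an item is binary or nominal there is no loss.

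Only secondary survey outcomes are touched. The primary endpoint, the prescription outcomes and the power calculation are unaffected, so this does not threaten the trial's main conclusion.

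**What to change.** In the statistical paragraph of Section 2:

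- Keep chi-square and Fisher's exact tests for binary and nominal responses. This includes the primary endpoint, prescriptions written and filled, and willingness if it is asked as yes/no.
- Compare one-week knowledge between arms as a single score, the number of knowledge items answered correctly, by Wilcoxon rank-sum test.
- Compare any item with ordered answers by Wilcoxon test or a proportional-odds model on all levels, and report the proportions alongside.

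The authors can check the attached questionnaires to see which clauses apply. If no item is ordered, the third is simply not used. Graded items outside the knowledge score would still be tested singly, so the change does not remove every item-level p-value.

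The cost is one or two sentences and a few lines of SAS, with no new data or participants. A score difference or common odds ratio is slightly less direct to read than a difference in proportions, which is why the proportions should stay in the report.

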### 3. STUDY PROCEDURES

After screening for HIV-negative patients ages 18-25 waiting to be seen by providers at Project Stay, informed consent will be given about the study. If the patient decides to participate in the study and agrees to the informed consent, the initial survey will be distributed either in hard-copy form or on an iPad (using a computer-assisted self-interview assessment) to obtain the data. Following the survey, the counselor will see whether or the patient is MSM, and perform stratified randomization based off this demographic. A third-party statistician will provide assignments in premade envelopes assigning participants based off blocked and stratified randomization to each arm of the study, which will not be opened until the participants has completed the survey. If the participant is assigned the control arm,

s/he will receive a pamphlet on the recent PrEP studies and asked to read over the information prior to seeing their provider. If the participant is assigned the interventional arm, the counselor will provide a one-on-one session on the recent PrEP results and answer any questions they might have, in addition to receiving the aforementioned pamphlet. All participants will then be asked to bring a sealed envelope to the provider, which will have three questions that the provider will fill out after their encounter with the patient:

1. Did the patient ask you about PrEP?
2. Did you bring up the subject of PrEP with the patient?
3. If yes to either, approximately how much time did you spend talking to the patient about PrEP?
4. Did the patient ask for a prescription for PrEP?

One week following the initial survey, participants will be contacted via e-mail about completing the final part of the study, which will include some of the same questions regarding knowledge, attitudes, and willing to use PrEP, as well as acceptability of other HIV prevention methods. This survey will be given using Survey Gizmo, a secure online survey provider service. Reminder e-mails will be sent up to 3 times, with a phone call follow up if the survey has not yet been completed. Participants will received a \$5 gift certificate to either Starbucks or McDonalds for completing the first portion of the study, and another \$5 gift certificate for completing the second/final part of the study.

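### The tests named for comparing the arms ignore the MSM strata used for randomisation; one stratified test should decide the primary endpoint

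*Protocol*

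**What the plan says.** All references are to the protocol.

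- **Tests.** Section 2 says that chi-square and Fisher's "exact tests will be computed to compare pamphlet-educated" and counselled participants on their survey answers and prescriptions. No rule says when each test applies.
- **Primary endpoint.** Section 2: "The primary endpoint is the difference between the proportion of participants who asked their providers about PrEP in the intervention group versus control group". The datum comes from the provider's form in Section 3 ("Did the patient ask you about PrEP"), not from the participant survey. For outcomes of this kind Section 2 says only that they "will be evaluated using a proportion and compared between groups".
- **Randomisation.** Sections 2 and 3 describe blocked randomisation stratified by whether the participant is MSM. The assignments sit in envelopes prepared by a third party.
- **Power.** Section 2 fixes the size by its "limited ability to survey 100 participants (50 in each group"). With an intervention proportion of .74, alpha .05 and power .80, it sets detectable limits on the share of participants "who ask their provider about PrEP in the control group is < .46 (or > .96"), and gives .28 as the least detectable difference. The test behind these limits is not named.

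**The concern.** The design separates participants by MSM status before assigning them, presumably because MSM status is expected to matter for interest in PrEP. A test on the pooled 2 x 2 table puts the between-stratum variation back into the error term, although blocking has already removed it from the comparison. If the strata do differ, the unstratified test rejects less often than 5% under the null and has less power than the same data allow. With a sample fixed at 100 by feasibility, power that costs no participants is worth having.

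A smaller matter is that the power paragraph does not say which test its limit belongs to, and the two named tests do not share one limit at 50 per arm.

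**Working it through.** **1. The plan's own figure.** Inputs from Section 2: n = 50 per arm, p1 = .74, p2 = .46, alpha .05. Two-sided testing is assumed, since a lower and an upper limit are both given. The uncorrected pooled formula is

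power = Φ[(|p1 − p2| − 1.96·√(2p̄(1−p̄)/n)) / √((p1(1−p1) + p2(1−p2))/n)].

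- p̄ = .60, so the null SE is √(2·.60·.40/50) = .0980.
- The alternative SE is √((.1924 + .2484)/50) = .0939.
- (.28 − 1.96·.0980)/.0939 = .937, which gives power 82.6%.
- At .47 the formula gives 79.8%; the 80% point is .469.

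So .46 is the last two-decimal value with at least 80%, and the lower limit and the .28 reproduce. The upper limit does not come from the same formula, which gives .942 rather than .96.

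**2. Exact power by test, no stratum difference.** Enumerating all 51 x 51 = 2,601 tables at .74 against .46 gives Pearson 83.2% and Fisher 77.5%. Fisher reaches 80% at a control proportion of about .452 (80.5% at .45). Its limit would therefore be about .45 and the difference about .29.

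**3. Effect of the strata.** Assumptions, none given in the protocol: half the sample is MSM, so 25 per arm per stratum, and the risk difference is .28 in both strata.

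- Strata 30 points apart: intervention .89 and .59, control .61 and .31.
- Strata 40 points apart: intervention .94 and .54, control .66 and .26.

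The CMH statistic without continuity correction is [Σ(a − m/2)]² / ΣV, with V = 25·25·m(50−m)/(50²·49). In each stratum, a is the number of askers in the intervention arm and m the number in both arms. It is compared with 3.84. Enumerating all 26⁴ outcomes gives:

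| Stratum gap | CMH | Pearson | Fisher |
|---|---|---|---|
| 0 | 83.3% | 83.2% | 77.5% |
| 20 points | 84.3% | 83.8% | 78.0% |
| 30 points | 86.5% | 84.5% | 78.7% |
| 40 points | 89.9% | 85.6% | 79.7% |

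The reason is visible in the variances. The pooled test uses .60·.40 = .24. The within-stratum average is (.75·.25 + .45·.55)/2 = .2175 at 30 points and (.80·.20 + .40·.60)/2 = .20 at 40 points.

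Hand check at 40 points, with alternative SE √((.1524 + .2084)/50) = .0849:

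- CMH: (.28 − 1.96·√(2·.20/50))/.0849 ≈ 1.23, about 89%.
- Pearson: (.28 − 1.96·.0980)/.0849 ≈ 1.04, about 85%.

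**4. Size under the null.** With both arms at .60 and a 40-point gap, true size is 5.0% (CMH), 3.3% (Pearson) and 1.9% (Fisher). With no gap it is 5.2%, 5.2% and 3.2%.

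**5. Sensitivity.** With a common odds ratio instead of a common difference (control strata 30 or 40 points apart, the same .74 and .46 overall), CMH has 85.5% and 88.0%, against 84.2% and 85.0% for Pearson. A continuity-corrected CMH would give the gain away: 80.9% and 84.9% in the 30- and 40-point cases of step 3.

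**The case against.** **The protocol may leave this to an analysis plan.** An unseen plan could specify a stratified test, and an unstratified test after stratified randomisation is not invalid. Both points stand. The protocol is not silent, however: it names tests, and neither takes account of the strata. Its logistic regression does not fill the gap. That model concerns willingness to use PrEP and selects its variables by significance, so MSM status is not guaranteed a place and the primary endpoint is not its outcome.

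**The gain is conditional.** This also stands. It is 2 points at a 30-point gap, about 4 at 40 points, and half a point at 20. The protocol gives neither the MSM share nor the gap.

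**A reader might infer that the primary result can receive two verdicts.** At 50 per arm, 94 of the 2,601 tables are significant by chi-square and not by Fisher; for example, 37/50 against 27/50 gives p = .037 and .060. The documents do not support making this the main point:

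- The sentence naming both tests covers survey responses and prescriptions. Its reach to the provider-reported endpoint is an inference.
- Naming the two together is common shorthand for Fisher when counts are small. At the design values the smallest expected count is 50·(1 − .60) = 20, so chi-square would apply, although the protocol does not write that rule down.
- All 94 disagreements go the same way, so taking the smaller p-value is the same as using chi-square, whose size is at most 5.7%. Disagreement occurs in 5.7% of trials at .74 against .46.

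**A reader might also infer that the stated 80% power fails.** It does not. The text says below .46, the figure reproduces under the uncorrected formula, and under Fisher the limit moves by only about .01.

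**Conclusion.** The point holds as a worthwhile improvement, not as an error that invalidates the analysis. The trial stratifies by MSM status, and the only two-group tests the protocol names ignore it. If the strata differ by 30 to 40 points and half the sample is MSM, the CMH test has 86-90% power, against 84-86% for Pearson and 79-80% for Fisher. It also keeps its size near 5% where the others fall below it. With no stratum difference CMH and Pearson are equivalent, so nothing is risked. The fault of the unstratified tests is conservatism; ignoring the strata does not inflate type I error.

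The figures assume balanced strata of 25 per arm, .74 against .46 overall, and two-sided .05. A smaller gap gives a smaller gain. The unnamed test behind the .46 limit is a secondary matter of clarity.

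**What to change.** In Section 2:

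- Name the CMH test stratified by MSM status as recorded at randomisation, two-sided .05 and without continuity correction, as the single decisive test for the primary endpoint.
- Report the MSM-stratified difference in proportions with its 95% CI.
- Reserve Fisher's exact test for sparse outcomes, such as prescriptions, by a stated rule (for instance an expected count below 5).
- In the power paragraph, say that the .46 limit and the .28 difference rest on the two-sided uncorrected chi-square formula. Correct or drop the .96 limit, which that formula does not give.

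The cost is a few sentences. MSM status is already collected before the envelope is opened, so no participants, visits or data items are added. The .46 limit can stay, since CMH has 83.3% exact power there even if the strata do not differ.
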